10.4. Safety Analyses

10.4.1. Adverse Events

The incidence of all TEAEs will be tabulated by cohort. These TEAEs will be classified by system organ class and preferred term or by preferred term in descending order of frequency using the Medical Dictionary for Regulatory Activities (MedDRA). For incidence reporting, if a subject reported more than one AE that was coded to the same system organ class or preferred term, the subject will be counted only once for that specific system organ class or preferred term. An overview of AEs, which includes subject incidence of TEAEs, TEAEs by severity, related TEAEs, related TEAEs by severity, SAEs, deaths, and AEs leading to discontinuation, will be presented.

10.4.2. Clinical Safety Laboratory Results

The observed data and change from baseline for each measurement day will be summarized with descriptive statistics.

Where criteria are available, laboratory values will be assigned toxicity grades, using NCI CTCAE v5.0. Directional shifts in laboratory toxicity grades (comparing baseline grade with worst post-baseline grade) will be analyzed using standard shift tables, presenting number and proportion of subjects and their maximum grade shift.

10.4.3. Vital Signs

The observed data and change from baseline for each measurement day will be summarized with descriptive statistics.

10.4.4. Electrocardiogram

The observed QTc data and change from baseline for each measurement day will be summarized with descriptive statistics.

10.5. Pharmacokinetic Analyses

For all monotherapy cohorts, the PK of voruciclib will be summarized by descriptive statistics. Pharmacokinetic parameters will be estimated, where appropriate, by non-compartmental analysis using statistical computer packages as specified in the statistical analysis plan. Graphic evaluation will be used for data analysis where appropriate. Pharmacokinetics and fit will be evaluated graphically; modeling will also be used if sufficient data are available.

For the combination treatment cohorts, the PK of voruciclib and venetoclax will be summarized separately, as above and compared to historical data.

10.6. Efficacy Analyses

For the Efficacy population, response to treatment will be tabulated with 95% exact binominal CIs.

The Kaplan-Meier method will be used to estimate PFS and DOR within subjects of the same tumor type. For PFS, subjects without documented progression will be censored at the date of last disease assessment.

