10.2. Study Endpoints

The primary study objectives are to determine the safety and tolerability and safe and mBED of voruciclib monotherapy in subjects with relapsed and/or refractory B-cell malignancies and AML and to determine the safety, tolerability and safe and mBED of voruciclib in combination with venetoclax in subjects with relapsed and/or refractory AML.

Safety will be assessed by AEs graded according to NCI CTCAE v5.0; laboratory safety tests including hematology (CBC), serum chemistry; physical examination; vital signs; ECOG performance status; and triplicate 12-lead ECG. If 2 or more of 6 subjects experience a DLT in a dose cohort, then the next lower dose will be the MTD.

The primary endpoint is:

- The incidence of AEs, including DLTs.

Secondary endpoints are:

- Efficacy endpoints within each tumor type:
 - a. Overall Response Rate (ORR), defined as the proportion of subjects who achieve a best overall response of
 - CR, CRi, or PR, with responses defined per 2008 International Workshop on CLL (IWCLL) guidelines,
 - CR or PR by 2014 Lugano criteria for non-Hodgkin lymphoma,
 - CR, CRi, CR_{MRD}, MLFS by the 2017 ELN criteria for AML
 - b. DOR defined as the time from first achieving a response to date of documented disease progression or death from any cause. Subjects who die due to any cause prior to progression will be censored
 - c. PFS defined as time from first dose of study drug to date of documented disease progression or death from any cause
 - d. Estimates of the exposure and association with efficacy and safety variables for voruciclib administered as monotherapy, and the PK of voruciclib and venetoclax when administered in combination

The exploratory endpoints are:

- a. Effects on biomarkers and functional activities of proteins in the apoptotic pathway
- b. Correlations of anti-tumor activity and baseline tumor characteristics

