**Table 5-1: Date of Progression or Censoring for DOR**

| Situation                    | Date of progression or censoring                                   | Outcome |
|------------------------------|--|---------|
| Disease progression or death | Date of death or date of disease assessment (planned or unplanned) | Event   |

|  |  |          |
|--|--|----------|
|  | showing disease progression, whichever occurs first                          |          |
| Subsequent anticancer treatment started before the first disease progression | Date of last disease assessment prior to the subsequent anticancer treatment | Censored |
| Alive and without disease progression on or before the EOS visit             | Date of last disease assessment  | Censored |

- Progression-Free Survival (PFS) defined as time from first dose of study drug to date of documented disease progression or death due to any cause. PFS will be calculated as follows:

$$\text{PFS (months)} = (\text{Event/Censoring Date} - \text{Date of the First Dose} + 1) / 30.4375$$

PFS will be right-censored for subjects who met one or more of the following conditions:

- subsequent anticancer therapy in the absence of documented disease progression
- alive and without documented disease progression on or before the EOS visit

If a subject meets more than one of these conditions, then the scenario that occurs first will be used to determine PFS. The event or censoring date will be determined based on the conventions listed in Table 5-2:

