**Table 5-2: Date of Progression or Censoring for PFS**

| Situation  | Date of progression or censoring   | Outcome  |
|--|--|----------|
|  |  |          |
| Death or disease progression   | Date of death or first disease assessment (planned or unplanned) showing disease progression, whichever occurs first | Event    |
| No evaluable disease assessments   | Date of the first dose   | Censored |
| Subsequent anticancer treatment started before the first documented disease progression or death | Date of last disease assessment prior to the subsequent anticancer treatment   | Censored |
| Alive and without disease progression on or before EOS visit                                     | Date of last disease assessment  | Censored |

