## 10. CHANGES FROM THE PROTOCOL SPECIFIED ANALYSES

No changes have been issued or planned.

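### PFS counts death as an event, but the protocol's censoring sentence does not exempt deaths and SAP Table 5-2 does not rank its no-assessment row against its death row

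*Protocol*

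**What the plan says.** **Definition.** Protocol 10.2: "PFS defined as time from first dose of study drug to date of documented disease progression or death from any cause". SAP 5.1.2 agrees: "Progression-Free Survival (PFS) defined as time from first dose of study drug to date of documented disease progression or death due to any cause".

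**Protocol censoring.** Section 10.6, repeated in the Synopsis under Statistical Analysis: "For PFS, subjects without documented progression will be censored at the date of last disease assessment". Neither place makes an exception for subjects who died.

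**SAP censoring.** SAP 5.1.2 lists two censoring conditions for PFS. One is subsequent anticancer therapy without documented progression. The other is "alive and without documented disease progression on or before the EOS visit". It then adds: "If a subject meets more than one of these conditions, then the scenario that occurs first will be used to determine PFS".

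**SAP Table 5-2.** Row 1 (death or progression) is an event, dated as "Date of death or first disease assessment (planned or unplanned) showing disease progression, whichever occurs first". Row 2, "No evaluable disease assessments", is censored at the date of first dose. Row 2 is limited neither to living subjects nor to post-baseline assessments.

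**Analysis set.** SAP 8.6.2 runs efficacy analyses on the Efficacy Evaluable Set. SAP 6.3 admits to it subjects who complete the first scheduled evaluation, or who progress or die before it.

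**Declared departures.** SAP section 10: "No changes have been issued or planned".

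**The concern.** A subject who dies without documented progression is an event under Protocol 10.2 and a censored record under Protocol 10.6. It is not safe simply to read the word alive into 10.6, because Protocol 10.2 does deliberately censor deaths for DOR. A programmer therefore has a textual reason to take the PFS sentence at face value.

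The SAP's own gap is narrower, but it falls on the subjects who matter. A living, progression-free subject who never reaches the first evaluation is outside the Efficacy Evaluable Set. Apart from assessments that were done but not evaluable, the subjects who can reach row 2 are therefore mainly early deaths. The set keeps them on purpose, so they count as non-responders in ORR. Row 2, if applied, would remove the same subjects from the PFS risk set on Day 1. Two programmers could code one death differently, and the error can only make PFS look longer.

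**Working it through.** **No plan figure to reproduce.** The documents give no PFS median, event count, death rate or precision target. The check is a comparison of the rules, followed by an illustration of size under stated assumptions.

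**Step 1. Three records under each rule**

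| Record | Definition (Protocol 10.2, SAP 5.1.2) | Protocol 10.6, literal | SAP Table 5-2 |
|---|---|---|---|
| A. Death on Day 20, no post-baseline assessment | Event, Day 20 | Censored, with no post-baseline date to use | Row 1: event, Day 20. Row 2: censored at first dose |
| B. Stable at C2D1 (Day 29), death on Day 45, no new therapy | Event, Day 45 | Censored, Day 29 | Event, Day 45 (row 1) |
| C. Progression on Day 57 | Event | Event | Event |

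Record B is where the SAP resolves the protocol's contradiction. Record A is where the SAP leaves its own overlap.

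**Step 2. Does the SAP tie rule settle record A?** It refers to the conditions just listed in the text: subsequent therapy, and alive without progression. Neither death nor absence of assessments is on that list. The rule does not rank row 1 against row 2 in either direction.

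**Step 3. Size if the deaths are censored.** All hazards are assumptions.

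- True median PFS m; total hazard λ = ln 2 / m; death share f; λd = fλ for death and λp = (1 − f)λ for progression.
- Progression is dated at the next 28-day visit. V(t) is the last visit day at or before t. A month is 30.4375 days, as in the SAP.
- Deaths as events: S(t) = exp(−λd·t − λp·V).
- Literal 10.6: S(t) = exp(−λp·V), with deaths before the first visit taken as censored at the start.
- Row 2 applied to deaths before the first visit: S(t) = exp(−λd·(t − 28) − λp·V).

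Base case, m = 2 months and f = 25%: λ = 0.6931 / 60.875 = 0.011386 per day, λd = 0.002847, λp = 0.008540. The share dying before the first visit is 1 − exp(−28 × 0.002847) = 7.7%. At month 3, t = 91.31 and V = 84:

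- deaths as events: exp(−0.2599 − 0.7173) = 37.6%
- literal 10.6: exp(−0.7173) = 48.8%
- row 2: exp(−0.1802 − 0.7173) = 40.8%

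A simulation of 60,000 subjects on the same assumptions gave 37.5%, 48.6% and 40.6%. At month 6 (t = 182.6, V = 168) the formulas give 14.2%, 23.8% and 15.3%.

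Month-3 inflation in percentage points, literal 10.6 / row 2:

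| True median | f = 15% | f = 25% | f = 35% |
|---|---|---|---|
| 1.5 months | 6.4 / 1.8 | 11.3 / 3.0 | 16.8 / 4.3 |
| 2 months | 6.4 / 1.9 | 11.2 / 3.1 | 16.4 / 4.4 |
| 3 months | 5.7 / 1.7 | 9.9 / 2.8 | 14.2 / 4.0 |

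The ranges are about 6 to 17 points and about 2 to 4 points (simulation error took the latter to 5). At month 6 the row 2 effect is 0.5 to 2.1 points. The row 2 median is unchanged in 6 of the 9 scenarios. Where it moves (2.5 to 2.8 months in the base case), much of the shift comes from the 28-day visit grid.

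**Step 4. Hand check of the row 2 mechanism.** Take 12 subjects with 1, 2 or 3 deaths before C2D1 and no other event by Day 28. Day-28 PFS is 11/12 = 91.7%, 10/12 = 83.3% or 9/12 = 75.0% with deaths as events. It is 100% if they are censored on Day 1. This shows the mechanism only; the SAP plans no PFS display by cohort.

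**The case against.** **The SAP already counts deaths.** The SAP is the detailed analysis document, and it does not repeat the 10.6 sentence. A reader might infer from 10.6 that the plan removes deaths from PFS generally. The documents do not support that: under the SAP, a death after at least one evaluable assessment and before new therapy is an event. This stands, and it confines the SAP problem to record A.

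**The tie rule does not force Day 1 censoring.** A reader might also infer that the first-occurring-scenario rule sends record A to row 2. It does not (Step 2). This stands; the finding is an unstated precedence, not a rule that row 2 wins.

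**The larger figures belong to a rule the SAP does not carry, and all hazards are assumed.** Both points stand. The visit model probably also overstates deaths without documented progression. Protocol Appendix 3 lets the marrow be omitted when peripheral blood clearly shows progression, Appendix 4 accepts peripheral blasts and extramedullary disease, and Table 5-2 accepts unplanned assessments.

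**It would not flatter a toxic dose in any planned output.** SAP 7.7 and 8.6.2.2 report PFS by tumor type, regimen and overall, not by dose cohort, and on-study deaths are tabulated and listed separately (SAP 8.1). This stands; no dose-level PFS comparison is at risk.

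**What survives.** The protocol contradicts itself, the SAP departs from 10.6 without declaring it, and row 2 overlaps row 1 for early deaths.

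**Conclusion.** Wrong as written; severity minor to moderate. Protocol 10.6 and the Synopsis, taken literally, turn deaths that 10.2 defines as events into censored records. The SAP corrects this for most subjects but says in section 10 that nothing changed. It leaves subjects who die before any evaluable assessment matching both an event row and a censoring row.

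If those early deaths were censored under row 2, month-3 PFS would be too high by about 2 to 4 points; under the literal protocol sentence, by about 6 to 17. Both ranges assume constant hazards, a true median of 1.5 to 3 months, a 15 to 35% death share and 28-day visits, none of which the documents supply. PFS is a secondary, descriptive Kaplan-Meier endpoint in a study that the SAP calls exploratory. Dose selection rests on DLTs, ORR and trough concentration, and expansion stopping on toxicity counts. No dose, stopping or sample-size decision therefore depends on this.

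**What to change.** 1. **Protocol 10.6 and Synopsis.** Replace the sentence with: *Subjects who are alive and have no documented progression are censored for PFS at their last disease assessment; death from any cause is an event on the date of death.*
2. **SAP Table 5-2, row 2.** Limit it to subjects with no evaluable post-baseline assessment and no recorded death. State that row 1 takes precedence when death occurs before any subsequent anticancer therapy.
3. **SAP section 10.** If the protocol sentence is not amended, list the difference there so that it is clear which rule governs.

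The cost is wording only, with no new data, and it should be settled before database lock. Reported PFS may be slightly less favourable.

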11. REGULATORY AND REPORTING REQUIREMENTS

The study will be conducted according to the principles of the Declaration of Helsinki ([World Medical Association 2013](#)), the International Council for Harmonisation of Technical Requirements for Pharmaceuticals for Human Use (ICH), Guideline E6(R2): Good Clinical Practice ([ICH 2016](#)), and the requirements of all local regulatory authorities regarding the conduct of clinical trials and the protection of human subjects. The study will be conducted by scientifically and medically qualified persons and the rights and welfare of the subjects will be respected.

Each subject will provide written informed consent before any study-related tests or evaluations are performed.

11.1. Institutional Review Board (IRB)/Independent Ethics Committee (IEC)

Approval of this study will be obtained from an IRB/IEC prior to enrolling subjects and will be reviewed and approved on an annual basis by the IRBs/IECs representing the participating institutions. Such IRBs/IECs must be appropriately constituted and meet all requirements as described in Title 21, Part 56 of the Code of Federal Regulations. The review must include the

protocol, subject recruitment materials, the Investigator's Brochure, the ICF, any other study-related material that will be provided to subjects (including study drug compliance diaries). A copy of the Letter or Notice of Approval from the IRB/IEC must be received by the sponsor prior to shipment of drug supplies to the Investigator. The IRB/IEC membership list or Federal Wide Assurance (FWA) number must be submitted to the Sponsor with the written IRB approval, and lists must be updated, if applicable.

11.2. Public Clinical Trial Registry

This study will be listed on a public clinical trial registry such as www.clinicaltrials.gov, per applicable regulations.

11.3. Confidentiality

The Principal Investigator and designees, employees, and agents involved with this study will comply with relevant state and federal laws relating to the confidentiality, privacy, and security of subjects' health information. Data generated during this study or disclosed by the sponsor to the Investigator will only be used as appropriate for the execution, analysis, review, and reporting of this study. Such information shall not be used for any other purposes and will remain confidential.

In order to verify subject eligibility criteria and ensure ongoing subject safety during the study and preserve the integrity of study data, notwithstanding source data verification at the study site, the Sponsor/CRO may request to review subject source medical data. Should the Sponsor request copies of subject medical data, the rationale for such request will be ethically and scientifically justified. Such records will promptly be destroyed by the Sponsor/CRO when the purpose of the review has been met.

In order to ensure subject safety and in adherence with regulatory guidelines, personal medical information may be reviewed by the IRB/IEC, or regulatory authorities. Every reasonable effort will be made to maintain strict confidentiality.

Though the results of the study may be presented in reports, published in scientific journals, or presented at medical meetings; subject names or identifiers will never be used.

11.4. Financial Disclosure

Investigators must maintain compliance with the current FDA guidelines and regulations concerning financial disclosure.

11.5. Data Quality Assurance

Good Clinical Practice (GCP) guidelines regarding clinical data management practices and procedures are to be utilized to ensure accurate, consistent, and reliable data. The sponsor or designee will establish a Data Management Plan for this study.

12. DATA MANAGEMENT

12.1. Use of Electronic Case Report Forms

Study data will be stored and transmitted using eCRFs, with a system determined by the sponsor. The sponsor will provide secure access and eCRF completion guidelines, as well as study-specific training, as needed, to each site.

Data recorded in the eCRFs must be supported by information captured in source documents, which must be available at all times for inspection by authorized representatives of the sponsor, the FDA, or other regulatory agencies. The eCRFs must be completed as soon as possible after each study visit or contact.

12.2. Study Site Monitoring

A sponsor-designated study monitor will conduct a site initiation visit prior to study enrollment, a visit shortly after enrollment of the first subject, and periodic interim monitoring visits during the study, as per the study-specific monitoring plan.

The primary purposes of the site visits are to:

- Ensure the accuracy and completeness of eCRF entries, as verified against the source documentation
- Verify that the conduct of the study adheres to the written protocol approved by the IRB/IEC, as well as regulatory requirements
- Verify that regulatory and other study-related documentation is maintained and current
- Perform voruciclib study drug accountability (reconcile study drug receipt, storage, dispensing, and return records)

12.3. Record Retention

The Investigator will retain the records of the study for 2 years following the last date that a marketing application for voruciclib is approved in any ICH region, or if marketing approval is not obtained, for 2 years after the Investigational New Drug (IND) for voruciclib has been closed. The sponsor will notify the Investigators when study records retention is no longer required.

For studies conducted outside the US under a US IND, the Principal Investigator must comply with the record-retention requirements set forth in the US FDA IND regulations and the relevant national and local health authorities, whichever is longer.

The site will retain copies of all versions of the protocol, Investigator's Brochure, correspondence with the IRB/IEC (including submission and approval letters, approved ICFs), curricula vitae and medical licenses of the Investigator and sub-Investigator(s), Forms FDA-1572, correspondence, laboratory documentation (including accreditation documents, reference ranges, and manuals), Delegation of Authority Log (documenting procedures delegated by the Investigator to be performed by study staff), voruciclib study drug records (including receipt, storage, dispensing, and return records), source documents (including clinic charts,

medical records, laboratory results, radiographic reports), training records, screening/enrollment logs, monitoring visit logs, and study procedure manuals.

Should the Investigator leave the institution or otherwise withdraw from the investigation or should there be any changes in the archival arrangements for the study records, the sponsor will be notified. The sponsor will be notified of the identity of any individual assuming responsibility for maintaining the study records and the location of their storage. If no other individual at the investigational site is willing to assume this responsibility, the sponsor will assume responsibility for maintaining the study records.

13. AMENDMENTS TO THE PROTOCOL

Amendments will be originated and documented by the sponsor. Individual study sites should communicate requests for protocol amendments directly to the sponsor. The sponsor may be required to discuss potential protocol amendments with the appropriate regulatory agencies. Amendments shall only be implemented following the required regulatory and ethical review and approval. Protocol amendments also may require changes to the ICF.

14. PUBLICATION POLICY

The sponsor intends to publish the results of this trial as soon as possible following completion of data analysis. Data derived from the trial are the exclusive property of the sponsor. Authorship (both inclusion and sequence) will be determined by mutual agreement. In the event of a disagreement on authorship, the sponsor will serve as adjudicator.



Venclexta US Prescribing Information. North Chicago, IL: AbbVie Inc., and South San Francisco, CA: Genentech Inc.; 2022.

World Medical Association. World Medical Association Declaration of Helsinki: ethical principles for medical research involving human subjects. *JAMA*. 2013; 310(20): 2191–2194.

APPENDIX 1. SCHEDULE OF ASSESSMENTS – CLL/SLL, FL, MCL, MZL, DLBCL, AND HIGH-GRADE B-CELL LYMPHOMAS

	Screening ^b	Cycle 1				Cycle 2		Cycle 3	Cycle 4	Cycle 5	Cycle 6	Cycle 7 ^c	End of Study ^d
Day(s) ^a	-28 to -1	1 ^a	2	8	15	1	15	1	1	1	1	1	30 days (± 3 days) post last dose
Informed consent	X												
Medical history	X												
Physical examination	X	X				X						X	X
Symptom-directed exam ^e				X	X		X	X	X	X	X		
Vital signs ^f	X	X		X	X	X		X	X	X	X	X	X
Height ^f	X												
Weight ^f	X	X				X		X	X	X	X	X	X
ECOG performance status	X	X				X		X	X	X	X	X	X
Pregnancy test ^g	X	X				X		X	X	X	X	X	X
HIV testing ^h	X												
Hepatitis B and C testing ⁱ	X												
Blood for PD/biomarker assays		X***	X			X							
Bone marrow biopsy/aspiration*	X											X	X
Tumor biopsy** (optional)	X			X									
Cytogenetics (FISH) ^j	X												X
IgHV mutational testing ^k	X												
Adverse events ^l		X	X	X	X	X	X	X	X	X	X	X	X
Concomitant medication ^m	X	X	X	X	X	X	X	X	X	X	X	X	X
ECG ⁿ	X	X		X	X	X							X
CBC with differential ^o	X	X		X	X	X	X	X	X	X	X	X	X
Serum chemistry ^p	X	X	X	X	X	X	X	X	X	X	X	X	X
TLS risk assessment and monitoring ^p	X	X	X										
Immunoglobulin tests ^q	X	X										X	
Coagulation ^r	X		X		X	X		X	X	X	X	X	X
Urinalysis (Dipstick) ^s	X					X		X				X	X
Issue and assess compliance diary ^t		X				X		X	X	X	X	X	
Dispense voruciclib ^u		X				X		X	X	X	X	X	
PK Sampling (all subjects) ^v		X	X	X	X	X							
Disease assessment ^w	X							X				X	X

APPENDIX 1. SCHEDULE OF ASSESSMENTS – CLL/SLL, FL, MCL, MZL, DLBCL, AND HIGH-GRADE B-CELL LYMPHOMAS (CONTINUED)

Abbreviations: ALP = alkaline phosphatase; ALT = alanine aminotransferase; ANC = absolute neutrophil count; aPTT = activated partial thromboplastin time; AST = aspartate aminotransferase; BP = blood pressure; BUN = blood urea nitrogen; CBC = complete blood count; CLL = chronic lymphocytic leukemia; CR = complete response; CT = Computed tomography; ECG = electrocardiogram; ECOG = Eastern Cooperative Oncology Group; EOS = End of Study; FISH = fluorescence in situ hybridization; FL = follicular lymphoma; Hct = hematocrit; HCV Ab = hepatitis C virus antibody; Hgb = hemoglobin; HIV = human immunodeficiency virus; HR = heart rate; ICF = informed consent form; IgHV = immunoglobulin heavy-chain variable-region gene; INR = international normalized ratio; LDH = lactate dehydrogenase; MCH = mean corpuscular hemoglobin; PCR = polymerase chain reaction; PD = pharmacodynamic; PK = pharmacokinetic; PT = prothrombin time; RBC = red blood cell; SLL = small lymphocytic lymphoma; TLS = tumor lysis syndrome; WBC = white blood cell.

- a. **Cycle 1 Day 1 and Study Assessment Day(s)** – C1D1 and visits when blood for pharmacodynamic/biomarker studies are collected should be conducted Monday through Wednesday if possible so that specimens can be shipped for receipt no later than a Friday. There is ± 3 day window allowable for each clinic visit during Cycle 1. Following Cycle 1, the allowable window is up to 7 days prior and 2 days after the scheduled clinic visit and its associated assessments.
- b. **Screening** – Screening assessments are to be performed within 28 days of first dose of voruciclib. Laboratory assessments need not be repeated on Day 1 if performed within the prior 72 hours. Physical examination need not be repeated on Day 1 if performed within the prior 7 days. Some tests performed prior to obtaining ICF (e.g., CT scan, bone marrow biopsy) may not need to be repeated for the study as long as they were performed within the allowed screening window.
- c. **Cycle 7+ – Subjects who remain on study after 7 cycles should follow the following study visit procedures:**
 - For Cycles 8-12, and Cycles 14-18, study visit procedures from Cycle 6 should be performed
 - For Cycles 13 and 19, study visit procedures from Cycle 7 should be performed
 - Cycles after 19 should follow the same schedule as Cycle 7 assessments every 6 cycles
- d. **EOS** – The EOS visit will occur 30 days ± 3 days from the last day of voruciclib administration (or prior to starting a new treatment if urgent treatment is required).
- e. **Symptom-directed exam** – Performed only as needed/indicated, based on interim history.
- f. **Vital signs, Height, Weight** – includes systolic and diastolic blood pressure (BP), heart rate (HR) and body temperature. Height collected at Screening only.
- g. **Pregnancy test** – Serum pregnancy test in females of childbearing potential at screening, urine pregnancy test Day 1 of each cycle and at EOS.
- h. **HIV testing** – HIV antibody testing is required.
- i. **Hepatitis B and Hepatitis C testing** – Hepatitis B core antibody, surface antibody and surface antigen, and hepatitis C virus antibody (HCV Ab) tests are required. Hepatitis B polymerase chain reaction (PCR) is required if hepatitis B core antibody and/or surface antigen is positive. Hepatitis C PCR is required if HCV Ab test is positive.
- j. **Cytogenetics (FISH)** – For subjects with SLL, CLL only; perform cytogenetics (FISH) for del(13q), del(11q), del(17), trisomy 12, del(6q) performed on blood or biopsy specimen of histologically-confirmed CLL/SLL. To be repeated when subject achieves a CR. The result does not need to be available for enrollment or initiation of study treatment.
- k. **IgHV mutational testing** – For subjects with SLL, CLL only; perform IgHV mutational testing in the peripheral blood lymphocytes or biopsy specimen at any time prior to initiation of therapy (may be collected prior to study screening). The result does not need to be available prior to enrollment or initiation of study treatment.
- l. **Adverse events** – Recorded from the first dose of voruciclib and continue until 30 days after the last dose, or until a subsequent anti-cancer therapy is initiated.
- m. **Concomitant medications** – Recorded from 28 days prior to Cycle 1 Day 1 through 30 days after the last dose of voruciclib, or until a subsequent anti-cancer therapy is initiated.
- n. **ECG** – 12 lead ECGs performed in triplicate (approximately 2–5 minutes apart while the subject is resting) at screening, Day 1 (Pre-dose and 4 hours post-dose), Day 8 (24 ± 3 hours after the preceding last dose in Cohorts 9-11), Day 15 (Pre-dose and 4 hours post-dose in Cohorts 1-5, and 24 ± 3 hours after the preceding last dose in Cohorts 6-8), and a single triplicate ECG at Day 1 of Cycle 2, pre-dose, if possible, and EOS. Additional ECG's as clinically indicated. For Cycle 1, pre-dose ECG should be within the 2 hours prior to dosing and post-dose within a 30-minute window either side of the nominal time. When a PK blood draw is scheduled at the same time as ECG, the ECG should be performed first and as close as possible immediately followed by the PK draw.
- o. **CBC with differential** – WBC, ANC, RBC, Hgb, Hct, platelets, MCH, and differential.

APPENDIX 1. SCHEDULE OF ASSESSMENTS – CLL/SLL, FL, MCL, MZL, DLBCL, AND HIGH-GRADE B-CELL LYMPHOMAS (CONTINUED)

- p. TLS monitoring/ Serum chemistry** – Chemistry for monitoring of TLS risk (including potassium, uric acid, phosphorus, calcium and creatinine) will be performed as indicated in the TLS management plan (see [Appendix 9](#) and as clinically indicated. Subjects must be assessed for TLS risk during screening and before first dose of voruciclib (monotherapy) on cycle 1 Day 1. Standard chemistry panel to include glucose, BUN, creatinine, sodium, potassium, chloride, calcium, phosphate, uric acid, CO₂, ALP, AST, ALT, total bilirubin, total protein, albumin, LDH.
- q. Immunoglobulin tests** – Quantitative serum immunoglobulin levels (IgA, IgG, IgM) will be performed for subjects with SLL and CLL at screening, at Day 1 of Cycle 1, and then every 6 months.
- r. Coagulation** – aPTT, PT, and INR.
- s. Urinalysis** – Dipstick.
- t. Issue and Assess Compliance Diary** – Compliance diary to record voruciclib administration. Returned diaries assessed for study drug compliance. New compliance diary dispensed with each dispensing of voruciclib.
- u. Dispense study drug** – Voruciclib is administered orally once a day on an empty stomach at least 1 hour prior to food or 2 hours after food at approximately the same time each day. On days of PK sampling, subjects should be instructed not to take voruciclib until after the PK sample is collected (note that in Amendment 7, there is no dosing on Day 8 for the IS_{1w3w} and Day 15 for the IS_{2w,2w}). A compliance diary assessment and returned voruciclib drug accountability should be performed at each visit which includes voruciclib dispensing.

As of Amendment 7, voruciclib will be administered on an intermittent dosing schedule of 2 weeks on/2 week off (IS_{2w,2w}) or 1 week on/3 weeks off (IS_{1w,3w}), in the 28-day cycle. Note that voruciclib is taken daily on dosing days only, i.e., Days 1 through 14 for IS_{2w,2w}, and on Days 1 through 7 only on the IS_{1w,3w} regimen.

- v. PK sampling** – Pre-dose specimens should be within 2 hours of dosing and for post-dose within \pm 30 minutes) after dosing.
Cohorts 1-5:

- Cycle 1 Day 1: pre-dose (before voruciclib dose is taken); and at 4- and at 6- hours post-dose
- Cycle 1 Day 2: pre-dose (i.e., 24 hours after the Cycle 1 Day 1 voruciclib dose)
- Cycle 1 Day 8: pre-dose (24 hours after the preceding last dose, before voruciclib is taken)
- Cycle 1 Day 15: pre-dose (before voruciclib dose is taken); at 4- and at 6- hours post dose

Cohorts 6b-11b (IS dosing):

- Cycle 1 Day 1: pre-dose and at 4- and at 6- hours post-dose
- Cycle 1 Day 2: pre-dose (24 hours after the preceding last dose)
- Cycle 1 Day 8: pre-dose (24 hours after the preceding last dose)
- Cycle 1 Day 15: (24 hours after the preceding last dose), if applicable [Day 15 samples only collected for the IS_{2w,2w} schedule]
- Cycle 2 Day 1: pre-dose

- w. Disease assessment** – Scans, bone marrow aspirate/biopsy and laboratory evaluation as appropriate for individual subjects. Scans to be performed at baseline within 3 months of Cycle 1 Day 1 and after termination of prior therapy, Cycle 3 Day 1, Cycle 7 Day 1, every 6 cycles thereafter, and upon permanently stopping study treatment. Response assessments for CLL/SLL and FL and other B-cell lymphomas, refer to [Appendix 5](#) and [Appendix 6](#), respectively.

- * Bone marrow – Biopsy/aspirate are required for assessment of response (as described in [Appendix 5, Table 19](#), and [Appendix 6, Table 21](#)) and as clinically indicated. Bone marrow biopsies may not need to be repeated for the study as long as they were performed within the allowed 28-day screening window. Additionally, optional biopsy/aspirates pre-first dose, at the end of cycle 6 and at end of treatment may be conducted for correlative studies. See Laboratory Manual.
- ** Tumor biopsy – tissue can be collected after completion of prior therapy and within 3 months of Cycle 1 Day 1 per Site Laboratory Manual. Formalin fixed material acceptable although fresh tissue preferred. Both the initial and repeat biopsy at Cycle 1 Day 8 are **optional**.
- *** For Cohorts 6b-8b, the first blood specimen for Pharmacodynamic /Correlative studies must be taken prior to first dose on Cycle 1 Day 1, a second specimen approximately 6 hours post dose on Day 1, and a third specimen pre-dose on Day 2. The specimen obtained prior to starting study drug may be taken up to 7 days prior to Cycle 1 Day 1. On Cycle 1 Day 15, a specimen will be taken prior to administration of study drug.

